### 5.3. Randomization

This is a randomized, double-blind, placebo-controlled study. Eligible participants will be randomized 1:1 to receive SAGE-718 or placebo for 84 days ( $\pm$ 7 days).

Randomization will be performed centrally via an interactive response technology (IRT) system. Randomization schedules will be generated by an independent statistician. The allocation to treatment group will be based on the randomization schedule.

# 5.4. Blinding and Unblinding

Participants, clinicians, and the study team will be blinded to treatment allocation. The randomization schedules will be kept strictly confidential, accessible only to authorized personnel until the time of unblinding. The blinding of the study will be broken after the database has been locked for the final analysis. In addition, only the designated personnel approved by Sage will be unblinded to the treatment allocation for the participants included in the IA, should one occur.

During the study, the blind can be broken by the investigator via the IRT system only when the safety of a participant is at risk and the treatment plan is dependent on the study treatment received. Unless a participant is at immediate risk, the investigator should make attempts to contact Sage prior to unblinding the study treatment administered to a participant. The responsibility to break the treatment code in emergency situations resides solely with the investigator. If the unblinding occurs without Sage's knowledge, the investigator must notify Sage within 24 hours of breaking the blind. All circumstances surrounding a premature unblinding must be clearly documented in the source records. In the case of emergency unblinding, the Early Termination Visit should be completed after a participant's treatment assignment has been unblinded.

If a participant becomes unblinded to the participant's treatment assignment before database lock, the participant will be excluded **and the second s** 

# 6. **MODIFICATIONS**

# 6.1. Modifications from the Approved Clinical Study Protocol Not applicable

# 6.2. Modifications from the Approved Statistical Analysis Plan

This is the first version of the SAP.

# 6.3. Modifications from the Approved DMC Charter

Not applicable

# 7. ANALYSIS SETS

# 7.1. Randomized Set

The Randomized Set will include all participants who have been randomized to the investigational product (IP) and will be used to describe participant's background characteristics.

# 7.2. Safety Set

The Safety Set will include all participants who were administered at least 1 dose of the IP. The Safety Set will be used to describe the safety data and analyses will be based on the actual treatment received.

# 7.3. Full Analysis Set

The Full Analysis Set (FAS) will include all participants in the Safety Set who have baseline and at least 1 post-baseline efficacy evaluation. FAS will be used to describe the efficacy data, which is based upon the Intent-to-Treat principle. Analyses will be based on the randomized treatment.

7.5.	

# 8. STATISTICAL ANALYSIS

# 8.1. General Considerations

Continuous data will be summarized in terms of the number of participants, mean, standard deviation (SD), minimum value (min), maximum value (max), median, 25th percentile (Q1), and 75th percentile (Q3). The minimum and maximum will be reported with the same number of decimal places as the source (raw) data. Mean, Least squares Means (LSM), median, Q1 and Q3 will be reported to 1 decimal place more than the source (raw) data. SD and standard error (SE), if applicable, will be reported to 2 decimal places more than the source (raw) data. Any values that require transformation to standard units (metric or SI) will be converted with the appropriate corresponding precision. Confidence intervals (CI) will be presented to one more decimal place than the associated parameter estimate. In general, the maximum number of decimal places reported shall be four for any summary statistic.

Categorical data will be summarized in terms of the number of participants providing data at the relevant time point (n), frequency counts, and percentages. Percentages will be presented to 1 decimal place unless otherwise specified. Any planned collapsing of categories will be detailed in the SAP text and the data displays.

Percentages will not be presented for zero counts. Percentages will be calculated using the number of participants (n) as the denominator. A missing category shall be included only for categorical variables where no data is available. The missing category will be omitted if there are no missing values for that variable.

Participants who are randomized to 1.2 mg treatment and received 0.9 mg dose due to dose reduction will be summarized under the same SAGE-718 treatment group. For efficacy data analysis, participants' data are analyzed by randomized treatment. For safety data analysis, participants' data are analyzed per the actual treatment received, and this is determined as follows: if a participant received any dose of SAGE-718 at any point of time, the participant is assigned to actual treatment of SAGE-718, regardless of the treatment to which the participant has been randomized.

All participant data, including those that are derived, that support the tables and figures will be presented in the participant data listings. Some data may be presented only in participant data listing, some may be presented with a corresponding table or figure; these will be indicated in relevant sections below. All summaries will be provided by treatment – either by randomized treatment or actual treatment received.

P-values will be reported to four decimal places, with p-values less than 0.0001 reported as "<0.0001". P-values larger than 0.9999 will be reported as ">0.9999".

Every attempt will be made to avoid missing data. All participants will be used in the analyses, as per the analysis populations, using all non-missing data available. No imputation process will be used to estimate missing data unless otherwise specified.

General definitions are defined as below:

• Baseline is defined as the last non-missing measurement prior to the first dose of IP, unless stated otherwise. If the time of an assessment is collected, baseline will be the

latest assessment prior to first dose of IP administration time; if the time of an assessment is not collected, the assessment on Day 1 is assumed to be prior to dosing as the protocol mentions that this assessment needs to be before dosing, or it is collected as "pre-dose".

- Study day 1 is defined as the date of randomization for untreated randomized participants or the date of first dose for treated participants.
- Study day will be calculated relative to the date of randomization for untreated randomized participants and relative to the date of first dose for treated participants.
  - If event is prior to randomization or the first dose, then study day is calculated as: Date of Event – Date of Randomization or First Dose
  - If event is on or after date of randomization or the first dose, then study day is calculated as:
     Date of Event Date of Randomization or First Dose + 1

8.2. Background Characteristics

## 8.2.1. Participant Disposition

This analysis will be based on all screened participants (i.e., all participants who have signed an informed consent).

Summaries will be provided for participants enrolled in the study including:

- Participants screened
- Participants screen-failed
- Participants screened but neither screen failed nor randomized Note: Due to enrolment closed, participants were discontinued from the study prior to inclusions/exclusions criteria reviewed
- Participants randomized
- Participants randomized but not dosed
- Participants received at least 1 dose of IP
- Number of participants randomized to placebo but received SAGE-718
- Participants who had dose reduction before Visit Day 42
- Participants completed IP
- Participants discontinued from IP and primary reasons for discontinuing IP
- Participants completed the study
- Participants discontinued from the study and primary reasons for early discontinuation

Numbers of participants and percentages for study or treatment completion or discontinuation as well as the reason for discontinuation will be based on the participants

who were randomized and received IP. Treatment arm assignment will be according to the randomized treatment.

In addition, summary of analysis sets including Safety Set, FAS, **settiment** will be provided for participants randomized. Treatment arm assignment will be summarized according to the randomized treatment.

If a participant is rescreened because the participant has been a screen failure the first time, the status of the participant will be determined from the second screening. In the count of screened participants, this participant will be counted only once.

Listings by treatment group will be provided for disposition of participants: screen failures and inclusion/exclusion criteria for all screened participants, and completion and discontinuation from study treatment and study participation, and inclusion in analysis sets for Randomized Set.

### 8.2.3. Demographics and Baseline Characteristics

This analysis will be based on the Safety Set and FAS.

Demographic data, such as age at randomization (continuous and categorical:  $\leq 65$ , >65), sex, childbearing status, race (both from CRF and derived categorical: Black or African American, White, Other), and ethnicity, years of education, years of employment, current employment status, and baseline characteristics, such as height, weight, and body mass index (BMI) will be summarized using descriptive statistics by treatment group and overall.

Baseline characteristics will also be summarized for:

• WAIS-IV Coding test score (continuous)

- WAIS-IV total correct Score (<Median, ≥Median)
- Clinical Dementia Rating (CDR) score (continuous)
- Clinical Dementia Rating (CDR) score (categorical: 0.5, 1)

- Divit (categorical.  $\leq 16.4$ , 16.5-24.9, 25-29.9,  $\leq 50$  K
- Years of Education (<Median, >Median)

Median categories are calculated from the overall baseline value and rounded to the nearest integer.

By-participant listing of all demographics and baseline characteristics will also be provided by treatment group for Randomized Set.

### 8.2.4. Medical/Surgical History

This analysis will be based on the Safety Set.

Medical history collected at screening will be coded using the Medical Dictionary for Regulatory Activities (MedDRA), Version 24.1 or higher. Medical history data will be summarized by system organ class (SOC) and preferred term (PT).

Medical history will be listed by treatment group. Also, by-participant listing of AD history will be provided separately. Listings will be provided for Randomized Set.

### 8.2.5. Prior and Concomitant Medications/Procedures

This analysis will be based on the Safety Set.

Medications and procedures will be recorded at each study visit during the study and will be coded using the World Health Organization Drug dictionary September 2021 B3, or later and MedDRA Version 24.1 or higher, respectively.

All medications/procedures taken within 30 days prior to Screening, all medications used to treat AD regardless of timing, and all nonpharmacological methods used to treat or prevent , or cognitive manifestations of AD are to be recorded. Those medications/procedures taken and ended prior to the first dose of IP will be denoted "Prior". Those medications/procedures taken prior to the first dose of IP and continuing beyond the initiation of the IP or those medications/procedures started at the same time or after the initiation of the IP will be denoted "Concomitant".

Medications/procedures will be presented according to whether they are "Prior" or "Concomitant" as defined above. If medication/procedures dates are incomplete and it is not

clear whether the medication/procedures are concomitant, it will be assumed to be concomitant.

Missing or partial dates will be imputed for medication/procedures. Algorithm for missing or partial start /end date is documented in Appendix C.

Concomitant medications/procedures are further categorized as on-treatment and post-treatment as follows:

- On-treatment concomitant medications/procedures are those that have been used between first and last dose of IP (both inclusive) as well as medications started prior to first dose of IP and continue beyond the initiation of IP.
- Post-treatment medications/procedures are those that have been started after the last dose of IP.

Concomitant medications will be summarized on the Safety Set using Anatomical Therapeutic Chemical (ATC) level 1 and Standard Medication Name by actual treatment group. Concomitant procedures will be summarized on Safety Set using System Organ Class (SOC) and preferred term by actual treatment group. By-participant listings of prior and concomitant (on-treatment and post-treatment) medications as well as procedures will also be provided for Randomized Set.

### 8.2.6. Investigational Product Exposure

Total drug exposure (in mg), total exposure duration to IP (in days), and percent of planned exposure received (in %) will be summarized for the Safety Set by actual treatment group.

Total drug exposure (in mg) is defined as the total IP in mg for SAGE-718 that was taken during the study. Total drug exposure for participants randomized to placebo is zero unless the participant has taken SAGE-718 by mistake, in which case the total exposure comes from SAGE-718 exposure and is summarized under SAGE-718 as the actual treatment. If a participant skips a dose on any of the days, the dose taken is 0 mg.

Total exposure duration to IP (in days) is defined as the date of the last dose minus the date of first dose plus 1. Note that this does not exclude days when the dose has been missed.

Percent of the planned exposure received is defined as the total drug exposure, divided by planned exposure, times 100.

- For participants who complete the treatment period, planned exposure is (Date of Day 42 visit First Dose Date of 1.2 mg + 1) times 1.2 mg for participants randomized to SAGE-718 plus (Date of Day 84 visit Date of Day 42 visit) times 0.9 mg for participants randomized to SAGE-718. For 0.9 mg exposure, with consideration of the Day 84 visit windows (+/- 7 days),
  - If Study Day of Day 84 Visit > 91, use the First Dose Date of 1.2 mg + 90 instead of Date of Day 84 visit. i.e. (Date of Day 84 visit Date of Day 42 visit) = First Dose Date of 1.2 mg + 90 Date of Day 42 visit.

- If Study Day of Day 84 Visit < 77, use the First Dose Date of 1.2 mg + 76 instead of Date of Day 84 visit. i.e. (Date of Day 84 visit Date of Day 42 visit) = First Dose Date of 1.2 mg +76 Date of Day 42 visit.

- For participants who discontinue the treatment prior to Day 42 visit, the planned exposure is (Last Dose Date First Dose Date + 1) times 1.2 mg for participants randomized to SAGE-718.
- For participants who discontinue the treatment on or after Day 42 visit but prior to Day 84 visit, the planned exposure is (Date of Day 42 visit – First Dose Date of 1.2 mg + 1) times 1.2 mg plus (Last Dose Date of 0.9 mg – Date of Day 42 visit) times 0.9 mg for participants randomized to SAGE-718.
- For participants who cannot tolerate 1.2 mg prior to Day 42 visit therefore received 0.9 mg for the remainder of the treatment period, the planned exposure is (First Dose Date of 0.9 mg First Dose Date of 1.2 mg) times 1.2 mg plus (Date of Day 84 visit First Dose Date of 0.9 mg + 1) times 0.9 mg for participants randomized to SAGE-718. For 0.9 mg exposure, refer to the first bullet for participants who complete the treatment period.
- For participants who never received SAGE-718, this measure is not applicable.

By-participant listings of IP administration and exposure will also be provided including participant ID, date of dose, planned exposure (mg), and actual exposure (mg).

### 8.2.7. Investigational Product Adherence

This analysis will be based on the FAS.

IP adherence (%) is defined as the number of capsules taken, divided by the number of capsules planned to be taken, times 100%. The planned number of capsules taken is defined as similar way as planned exposure, with consideration of the Day 84 visit windows (+/- 7 days).

- For participants who complete the treatment period, the planned number of capsules taken is defined as follows:
  - 77 if Study Day of Day 84 Visit < 77
  - (Date of Day 84 visit First Dose Date + 1) if Study Day of Day 84 Visit is between 77 and 91 (inclusive)
  - 91 if Study Day of Day 84 Visit > 91
- For participants who discontinue the treatment earlier than Day 84 Visit, the planned exposure is (Last Dose Date First Dose Date + 1).

Number and percentage of participants with IP adherence in categories (<80%, 80-100%, >100%) will be provided. By-participant listing of IP adherence will be provided.

# 8.3. Efficacy Analysis

The FAS will be used for all efficacy summary and analysis tables.

### 8.3.1. **Definition of Efficacy Variable(s)**

### 8.3.1.1. Primary Efficacy Assessment

The WAIS-IV Coding Test is a valid and sensitive measure of cognitive dysfunction impacted by many domains. In-clinic administration of the WAIS-IV Coding Test will use the traditional paper-and-pen format, in which the participant is required to identify the symbols matched to numbers using a key and write in the symbol beneath the associated number. The score is based on the total number of codes correctly completed over a 120 second time limit. The WAIS-IV Coding Test will be performed as outlined in Table 12.

8.3.1.2.3.4.	
8.3.1.2.3.5.	

### 8.3.2. Visit Windows for Efficacy Analyses

The scheduled visits will not be windowed and will be used at nominal visit value for analysis purposes. The unscheduled and early termination (ET) visit will be mapped to a scheduled visit for analysis. In order to accommodate as much data as possible into analysis, the executive windows have been defined as shown in below tables, which have been widened, compared to protocol-specified operational windows. These windows will be used for analysis purposes only. Once analysis visit windows are assigned, all visits, including scheduled visits, unscheduled visits, and ET visits will be eligible for being flagged as the "analyzed record" within the analysis window; a participant's individual analysis visit window could potentially contain more than 1 visit. In the event of multiple visits falling within an analysis window or in case of a tie, the following rules will be used in sequence to determine the "analyzed record" for the analysis visit window:

- If the data from the scheduled visit is available, then the scheduled visit data will be used.
- If no data from the scheduled visit is available, the data from unscheduled visit closest to the scheduled study day for that window will be used.
- If there is a tie before and after the scheduled day, the later data will be used.

Scheduled Visit	Target Study Day	Study Day Window for Visit in Analysis
Baseline	Day 1 (pre-dose)	Day 1 (pre-dose) or last non- missing assessment before the first dose of IP
Day 84 (±7 days)	Day 84	Day 64 – Day 98

#### Table 4. Analysis Visit Windows for WAIS-IV Coding Test

Table 6.

### 8.3.3. Analysis of Primary Efficacy Variable(s)

### 8.3.3.1. Primary Analysis and Estimand

The estimand for the primary efficacy analysis is defined as follows:

- 1) The treatment regimen for participants is placebo or SAGE-718 for 84 days.
- 2) The target population is adult participants with Mild Cognitive Impairment or Mild Dementia Due to Alzheimer's Disease.
- 3) The variable of interest is the change from baseline in WAIS-IV Coding test score at Day 84.
- 4) The intercurrent events could be:
  - a) The premature discontinuation of treatment for any reason. The treatment policy strategy will be used.
  - b) Taking certain medications including, but not limited to, medications with potent effects at the NMDA receptor, including memantine, amantadine, ketamine, or related compounds or other medications, given at doses, frequencies, or in combinations that are likely, in the opinion of the investigator, to have a deleterious effect on cognitive performance, or prescribed cannabis or other THC-containing substances. The treatment policy strategy will be used.
- 5) The population summary level deals with the difference between SAGE-718 and placebo treatments in mean change from baseline in WAIS-IV Coding test score at Day 84.

Participants will be analyzed according to randomized treatment. Descriptive statistics of WAIS-IV Coding test score, percent change from baseline and change from baseline will be summarized by treatment group and by visit.

The primary endpoint is change from baseline to Day 84 in the WAIS-IV Coding test and this primary endpoint will be analyzed using a mixed-effects model for repeated measures (MMRM). The model will include baseline WAIS-IV Coding test score as a continuous explanatory variable, treatment, visit, and visit-by-treatment interaction as categorical explanatory variables. The Kenward-Roger correction to degrees of freedom will be applied. All explanatory variables will be treated as fixed effects in the model, and all post-baseline time points will be included in the model. An unstructured (UN) covariance matrix with the default Newton-Raphson algorithm as implemented in the SAS procedure PROC MIXED will be used to model the within-subject correlation. If this model fails to converge, the Fisher Scoring algorithm (via the SCORING option of the PROC MIXED statement), the no-diagonal factor analytic structure (via the TYPE=FA0(T) option of the REPEATED statement, where Tis the total number of time points), Toeplitz (TOEP), Autoregressive (1) [AR (1)], Compound symmetry (CS) covariance structure will be used, following this sequence until convergence is achieved. If the model still does not converge with CS structure, no results will be reported. When the covariance structure is not UN, the sandwich estimator for the variance-covariance matrix will be derived, using the EMPIRICAL option in the PROC MIXED statement in SAS. The primary comparison will be between SAGE-718 and placebo at the Day 84. The LSM and SE with 95% CI for each treatment group as well as difference in LSM and SE with 95% CI will be summarized, and the p-value from the hypothesis test of no difference between the treatment groups will be also presented.

Descriptive statistics of WAIS-IV Coding test score, percent change from baseline and change from baseline will be summarized by treatment group and by visit.

Line plots with LSM and SE bars of change from baseline in WAIS-IV Coding test score over time by treatment group will be provided.

By-participant listing of WAIS-IV Coding test score by treatment group and by visit will be produced.

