## 7.2. Number of Participants

Approximately 150 participants will be randomized to obtain up to 60 evaluable participants per treatment arm. Additional participants may be randomized if the early discontinuation rate is higher than expected. If the early discontinuation rate is lower than expected, enrollment may be closed once 120 evaluable participants have completed the study.

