# 13.8. Sample Size and Power

The sample size calculation is based on change from baseline in WAIS-IV Coding Test total correct score. Based on data in a previous study, we assume difference between placebo and the SAGE-718 group at the end of treatment (at Day 84) for primary endpoints of WAIS-IV Coding test total correct score is 2.5, the standard deviation is 4.2.

The total sample size of 120 evaluable participants will provide 90% power to detect the treatment difference of 2.5 in change from baseline in WAIS-IV Coding Test total correct score while allowing for one interim analysis and one final analysis. This sample size and power are based on a two-sided test using an overall significance level of 0.05. One formal interim analysis may be conducted after approximately 60 participants have completed Week 12. The group sequential method by O'Brien and Fleming for the two-sided test will be used. The significance level will be based on the type I error spending function of Lan and DeMets such that the overall significance level will be maintained at 0.05. Assuming a 20% dropout and a 1:1 randomization ratio, approximately 150 randomized participants (75 per treatment group) will be required to obtain 60 evaluable participants per treatment group. Evaluable participants are defined as those randomized participants who receive IP and have a valid baseline and at least 1 postbaseline WAIS-IV Coding test assessment. Additional participants may be randomized if the dropout rate is higher than 20%.

Table 6 summarizes operating characteristics of this design based on 120 evaluable participants.

Repeated Analyses	Information Time	No of Participants	Boundaries for Efficacy	Boundary for Futility
Interim	0.5	60	2.796	0.4229
Final	1	120	1.977	

Table 6:	Group Sequential Design
----------	-------------------------

13.8.1.

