# 5.2. Sample Size and Power

The sample size calculation is based on change from baseline in WAIS-IV Coding Test total correct score. Based on data from a previous study (718-CNA-201), the assumed difference between placebo and the SAGE-718 group at the end of treatment (at Day 84) for the primary endpoint of WAIS-IV Coding test total correct score is 2.5, and the standard deviation is 4.2.

The total sample size of 120 evaluable participants will provide 90% power to detect the treatment difference of 2.5 in change from baseline in WAIS-IV Coding Test total correct score while allowing for 1 interim analysis (IA) and 1 final analysis. This sample size and power are based on a 2-sided t-test using an overall significance level of 0.05. One formal IA

may be conducted after approximately 60 participants as total have completed Day 84 (Week 12). The group sequential method by O'Brien and Fleming for the two-sided test will be used. The significance level will be based on the type I error spending function of Lan and DefsMets such that the overall significance level will be maintained at 0.05. Assuming a 20% dropout and a 1:1 randomization ratio, approximately 150 randomized participants (75 per treatment group) will be required to obtain 60 evaluable participants per treatment group. Evaluable participants are defined as those randomized participants who receive IP and have a valid baseline and at least 1 postbaseline WAIS-IV Coding test assessment. Additional participants may be randomized if the dropout rate is higher than 20%. Table 2 summarizes operating characteristics of this design based on 120 evaluable participants.

Repeated Analyses	Information Time	Number of Participants	Boundaries for Efficacy (Z-score)	Boundary for Futility (Z-score)
Interim	0.5	60	2.796	0.4229
Final	1	120	1.977	

Table 2:Group Sequential Design

\* Using the SAS Software Version 9.4

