# APPENDIX A. SCHEDULE OF ASSESSMENTS

### Table 12. Schedule of Assessment

Assessments	Screenin g Period	Baseline Period		Treatment Period					
	Days -35 to -8	Days -7 through -1	Day 1 a	Day 14 (±2 days)	Day 28 (±2 days) safety phone call b	Day 42 (±2 days) c	Day 63 (±2 days) safety phone call b	Day 84 (±7 days) d or ET	Day 112 (±7 days)
Informed consent e	X								
Inclusion/exclusion criteria	Х		Х						
Randomization			Х						
Medical history and demographics f	Х								
Participant training g		Х							
Body weight	X		X			Х		Х	X
Body height	Х								
CDR	Х								
Vital signs (including orthostatic) h	X		Х	Х		X		Х	X
Physical examination i	X		X	Х		Х		Х	Х
FSH test j	X								
Serology test k	X								

Assessments	Screenin g Period	Baseline Period			Treatr	nent Period			Follow-Up Period
	Days -35 to -8	Days -7 through -1	Day 1 a	Day 14 (±2 days)	Day 28 (±2 days) safety phone call b	Day 42 (±2 days) c	Day 63 (±2 days) safety phone call b	Day 84 (±7 days) d or ET	Day 112 (±7 days)
12-lead ECG 	х		Х	Х		Х		Х	Х
MRI m	Х								
Safety laboratory assessments n	х		Х	Х		Х		Х	Х
Urine drug test	х		Х	Х		Х		Х	х
Alcohol breath test	Х		Х	Х		Х		Х	Х
Pregnancy test o	Х		Х					Х	

Assessments	Screenin g Period	Baseline Period			Treatr	nent Period			Follow-Up Period
	Days -35 to -8	Days -7 through -1	Day 1 a	Day 14 (±2 days)	Day 28 (±2 days) safety phone call b	Day 42 (±2 days) c	Day 63 (±2 days) safety phone call b	Day 84 (±7 days) d or ET	Day 112 (±7 days)
WAIS-IV Coding test r		Х						Х	
IP self-administration u					X (once dail	y in the mornir	ng)		
IP dispensation v			Х	Х		Х			
IP accountability w						Х			
IP return x				Х		Х		Х	
Safety call assessment b					Х		Х		
AEs/SAEs y	X								
Prior and concomitant medications z					Х				

Abbreviations: AD = Alzheimer's Disease; AE = adverse event,

CDR = Clinical Dementia Rating;
COVID-19 = coronavirus disease 2019;
ECG = electrocardiogram; ET = early termination; FSH = follicle-
stimulating hormone; HIV = human immunodeficiency virus; ICF = informed consent form; IP = investigational product;
MRI = magnetic resonance imaging;

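### Does counting people with only an early-termination Coding score as evaluable undercut the 120 participants and the 90% power?

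*SAP*

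**What the plan says.** SAP 8.3.3.1 analyses change from baseline to Day 84 in WAIS-IV Coding with an MMRM and specifies: "All explanatory variables will be treated as fixed effects in the model, and all post-baseline time points will be included in the model". How many time points that means depends on the schedule. SAP 8.3.1.1 states: "The WAIS-IV Coding Test will be performed as outlined in Table 12". In that table the row "WAIS-IV Coding test" is marked at Baseline and in the combined Day 84 or ET column only, and Protocol Table 2 agrees. SAP 8.3.2 gives Coding one post-baseline window, study days 64 to 98, and says of off-schedule visits: "The unscheduled and early termination (ET) visit will be mapped to a scheduled visit for analysis".

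For sample size, Protocol 13.8 and SAP 5.2 call a randomised participant evaluable if they took IP and "have a valid baseline and at least 1 postbaseline WAIS-IV Coding test assessment". No timing is attached. SAP 5.2 continues: "Assuming a 20% dropout and a 1:1 randomization ratio, approximately 150 randomized participants (75 per treatment group) will be required" to reach 60 evaluable per arm. Two rules govern the numbers recruited. Protocol 13.8: "Additional participants may be randomized if the dropout rate is higher than 20" percent. Protocol 7.2: if discontinuation is lower than expected, "enrollment may be closed once 120 evaluable participants have completed the study".

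**The concern.** With one post-baseline time point, the visit terms and the sequence of fallback covariance structures have nothing to act on. The model is an ANCOVA of Day 84 change on treatment and baseline score, among those with a Day 84 record. Someone who leaves at, say, Day 30 and does the Coding test at the ET visit meets the definition of evaluable and belongs to the Full Analysis Set, but contributes nothing to the primary comparison.

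Three things could then be at stake.

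- The 120 and the 90% might describe a larger group than the one tested.
- The unconditional mapping sentence for ET visits might lead one programmer to carry a Day 30 score to Day 84 and another to drop it.
- The MMRM label might suggest that partial data from leavers support the missing-at-random assumption, when for Coding there are none.

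A related wording difference concerns intercurrent event 4a. Protocol 13.5 ties treatment discontinuation to the absence of a Day 84 score. SAP 8.3.3.1 omits that clause, and SAP 6.1 records no modification.

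**Working it through.** **1. The plan's own figure.** Inputs from SAP 5.2: difference 2.5, SD 4.2, two-sided 0.05, 1:1 allocation, 20% dropout.

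- n per arm = 2 × [(1.960 + 1.282) × 4.2 / 2.5]² = 59.3, rounded up to 60.
- At 60 per arm the noncentrality is (2.5/4.2) × √(60/2) = 3.26. Power is 89.9% by noncentral t and 90.3% by the normal approximation.
- With the interim and the tabulated efficacy bounds 2.796 and 1.977, power is 90.1% (89.1% if the futility bound is binding).
- Randomised: 120 / 0.80 = 150.

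The stated figures reproduce.

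**2. Who is in that 120.** At 20% dropout, 150 × 0.20 = 30 leave and all 30 are subtracted. If a fraction q of them had an early ET Coding test, the evaluable count would be 120 + 30q, while the number tested stays at 120. For q = 0.211, 0.444 and 0.706 the evaluable count is 126.3, 133.3 and 141.2. Power remains 89.9% in each case, so the loose definition inflates the label and not the test.

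**3. What a loss would require.** Suppose the evaluable count is exactly 120 and a share s of it has only an early ET score. The documents give no value for s, so these are assumed. At 20% dropout the fraction of leavers tested early is 4s/(1 − s), and the number randomised is the number tested divided by 0.80.

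| s | Tested, 120(1 − s) | Power (t) | Leavers tested early | Randomised |
|---|---|---|---|---|
| 0 | 120 | 89.9% | 0% | 150 |
| 5% | 114 | 88.3% | 21% | 142.5 |
| 10% | 108 | 86.5% | 44% | 135 |
| 15% | 102 | 84.5% | 71% | 127.5 |

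Each loss row needs recruitment to stop short of 150.

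**4. Whether the rules allow that.** Protocol 7.2 permits early closure only on evaluable participants who have completed the study. A completer has no ET visit, so the only scheduled post-baseline Coding test that can make a completer evaluable is Day 84. For this rule, evaluable and tested coincide. The top-up rule in Protocol 13.8 is keyed to the dropout rate. With 150 randomised and 30% lacking a Day 84 score because they left, 105 are tested (85.6% power), and 15 early ET tests among the 45 leavers would still show 120 evaluable. The trigger reads 30% against 20% regardless of that count. Finally, SAP 8.2.1 notes participants who were not randomised because enrolment had closed, so redefining the term in the SAP could no longer steer recruitment.

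**5. The early ET score.** SAP 8.3.2 keeps scheduled visits at their nominal label, assigns ET and unscheduled visits through the window table, and then picks an analysed record within the window. A Coding score before Day 64 falls in no window, so it yields no Day 84 record. The mapping sentence suggests otherwise only when read apart from the table that follows it.

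**6. Missing Day 84 scores.** Take an assumed case: 80% stay on IP, 5% stop but attend Day 84, 15% leave, and stoppers keep none of the benefit. The treatment-policy effect is 2.5 × 0.80 = 2.00. The observed-case estimate is 2.00/0.85 = 2.35. The excess of 0.35 is 0.48 of a standard error of 4.2 × √(2/64) = 0.74. If stoppers keep all of the benefit, the bias is zero. Calling the model ANCOVA changes none of these numbers. Protocol 13.2 and 13.5.2 already plan a multiple-imputation sensitivity analysis when more than 5% of either group lacks the primary endpoint. Below that trigger, with 3 of 75 per arm missing, the bias is 0.04 × 2.5 = 0.10 points if leavers keep no benefit.

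**The case for a change.** The strongest case for acting is that the definition and the test do not match, and aligning them costs only wording. The dropout arithmetic treats every leaver as not evaluable, while the definition keeps any leaver with an ET test, so SAP 5.2 is inconsistent with itself. The top-up rule is permissive, so 30% dropout could be left uncorrected. The missing-at-random assumption also rests only on arm and baseline score, and SAP 8.3.3.1 does not say so.

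The inconsistency stands as a matter of wording. So does the permissive top-up, but that weakness belongs to the word *may* and would remain under any definition of evaluable. The missing-data point is fair in principle. However, the section of the SAP where sensitivity analyses would sit (8.3.3.3) is blacked out, and the abbreviation list includes MAR, MNAR, multiple imputation and pattern mixture models. The public text cannot show that this is unaddressed. ANCOVA is also listed, although no visible method uses it. On event 4a, both documents apply the treatment-policy strategy to discontinuation, so the difference is editorial.

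**Conclusion.** The observation is correct and the consequence does not follow. On the public schedule, a participant whose only post-baseline Coding score precedes Day 64 is evaluable but outside the primary test. Under the plan's own 20% dropout, 120 participants still have Day 84 scores and power is about 90%. The falls to 88.3%, 86.5% or 84.5% rest on assumed shares, and on recruitment stopping early in a way Protocol 7.2 does not allow.

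The term appears only in the sample-size and participant-number text. It defines no visible analysis set, so rewording it would alter no visible analysis. The window table already settles early ET scores as a careful programmer would read it. The one-visit MMRM gives the same estimate as the ANCOVA, and a sensitivity analysis for missing scores is already planned. This is loose wording that analysts will fill sensibly, and no change is needed.

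The conclusion assumes that the Coding row is complete as shown (its footnote is hidden) and that the windows govern the ET mapping.
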